7.2.3 Secondary endpoint analyses

Key Secondary Endpoint Analysis

Primary Objective: Dose Finding

For the dose finding analysis of the study, there are no key secondary endpoints defined.

Secondary Objective: Formal Statistical Testing

For the formal analysis of the study, the treatment effect on the key secondary endpoint, the occurrence of at least one GPP flare up to week 48, will be tested in a hierarchical manner as a part of the pre-specified testing strategy, subsequent to the test of the primary endpoint, which is defined in [Section 7.1](#)

The stratified Cochran-Mantel-Haenszel (CMH) test will be performed for each dose of BI 655130 versus placebo stratified by the concomitant use of systemic GPP medications at randomization (yes or no), and based on the RS. The difference in the proportion of patients who do not experience a GPP flare, and the associated confidence intervals will be presented for each active group versus the placebo group using the Mantel-Haenszel type weighted average of differences using weights as proposed by Greenland & Robins [[R09-1299](#)].

Any use of rescue medication or investigator-prescribed SoC prior to the onset of the first GPP flare is considered to represent a failure, i.e. the onset of a GPP flare event. Furthermore, as described for the primary endpoint analysis, the key secondary endpoint analysis will also include both on- and off-treatment data of all patients up to Week 48.

The primary method for handling of missing data on the occurrence of at least one GPP flare is described in [Section 7.3](#).

Secondary analyses of the key secondary endpoint will be the same as those defined for the primary endpoint. In addition, a sensitivity analysis using a landmark test will be performed to evaluate treatment effects. This test will compare Kaplan Meier estimates at Week 48 between each dose of BI 655130 and placebo whereby the variance of each KM estimate is calculated by the Greenwood's formula. Further details for the landmark test will be described in the TSAP.

Secondary Endpoint Analysis:

For the formal analysis of the study, the treatment effect on the following secondary endpoints, 1) Time to first worsening of PSS up to week 48 (defined as a 4-point increase in total score from baseline), and, 2) Time to first worsening of DLQI up to week 48 (defined as a 4-point increase in total score from baseline), will be tested in a hierarchical manner as a part of the pre-specified testing strategy, subsequent to the test of the primary and key secondary endpoints, which is defined in Section 7.1.

The time to first worsening of PSS up to week 48, where any use of rescue medication or investigator-prescribed SoC prior to observing the endpoint is considered to represent a worsening of the PSS, will be tested for each dose of BI 655130 vs. placebo using the

stratified log rank test stratified by the factor, concomitant use of systemic GPP medications at randomization (yes or no) and based on the RS.

The time to first worsening of DLQI up to week 48, where any use of rescue medication or investigator-prescribed SoC will be considered to represent a worsening of the DLQI, will be analysed in the same manner as described for the time to first worsening of PSS.

Imputation rules of missing data for the above two secondary endpoints will be described in [Section 7.3](#).

All secondary endpoints will be descriptively displayed. Descriptive comparison for adults versus adolescents will be performed for secondary endpoints in the hierarchical testing. Statistical tests on the remaining secondary binary endpoints will be performed as described for the key secondary endpoint.

7.2.5 Safety analyses

Adverse events will be coded using the current version of Medical Dictionary for Regulatory Activities (MedDRA) coding dictionary. Standard BI summary tables and listings will be produced.

All treated patients will be included in the safety analysis. In general, safety analyses will be descriptive in nature and will be based on BI standards. No hypothesis testing is planned. Statistical analysis and reporting of adverse events will concentrate on treatment-emergent adverse events. To this end, all adverse events occurring between start of treatment and end of the residual effect period will be considered 'treatment-emergent'; the residual effect period (REP) is defined as 16 weeks after the last dose of trial medication. Note that for patients who continue into the extension trial (1368-0025), all TEAE up to the time-point of first dose of the trial medication in the extension trial will be available for display in the current study. Adverse events that start before first drug intake and deteriorate under treatment will also be considered as 'treatment-emergent'. For all subjects who received rescue medication with BI 655130, safety assessments including adverse events, laboratories, vital signs etc. which occurred subsequent to such intake will be excluded from presentations according to the planned treatments; these data will, however, be included in summaries where all data after any use of BI 655130 are displayed.

Frequency, severity, and causal relationship of adverse events will be tabulated by system organ class (SOC) and preferred term after coding according to the current version of the MedDRA at database lock.

The exposure adjusted incidence rate (per 100 subject years) of a selected treatment emergent adverse event is defined as the number of subjects experiencing the adverse event per

treatment group during time at risk divided by the total time of subjects at risk in that treatment group to contribute the event to the analysis multiplied by 100 (per 100 subject years), where:

$$\text{Time at risk [subject years]} = (\text{date of onset of TEAE} - \text{study drug start date} + 1) / 365.25$$

[figure not shown]
If, for a subject, the selected treatment emergent adverse event didn't occur then the time at risk will be censored at min (date of death, [for patients who didn't roll over to the extension trial] last contact date per EoS page, [for patients who roll over into the extension trial] date of first dose in extension trial – 1 day, drug stop date + 112 days, date of rescue medication of BI 655130). For each selected treatment emergent AE, the exposure adjusted incidence rate will be calculated as:

$$\text{Incidence rate [1/100 Subject years (pt-yrs)]} = 100 * \text{number of subjects with AE} / \text{Total AE-specific time at risk [subject years]}.$$

Laboratory data will be analysed both quantitatively as well as qualitatively. The latter will be done via comparison of laboratory data to their reference ranges. Values outside the reference range as well as values defined as clinically relevant will be highlighted in the listings. Treatment groups will be compared descriptively with regard to distribution parameters as well as with regard to frequency and percentage of patients with abnormal values or clinically relevant abnormal values.

Vital signs, physical examinations, or other safety-relevant data observed at screening, baseline, during the course of the trial and at the end-of-trial evaluation will be assessed with regard to possible changes compared to findings before start of treatment.

Immunogenicity data will be analysed in a descriptive way.

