### 6.6.3 Safety data

It is not planned to impute missing values in safety evaluations.

For the descriptive reporting of safety data by visit, the data available on each visit will be summarized for the randomized maintenance treatment period, flare treatment period, and OL maintenance treatment period, respectively.

For safety data that is not collected by visit such as AE and possibly clinically significant laboratory abnormality, the original results (OR) to be used for the descriptive reporting for corresponding treatment periods.

The only exceptions where imputation might be necessary for safety evaluation are AE dates and, start and stop dates for concomitant medications. Missing or incomplete AE dates are imputed according to BI standards (see *BI-KMED-BDS-HTG-0035* (4)).

Partial start and stop dates for concomitant medications, and background, investigator-prescribed SoC, as well as historical medication for GPP will be imputed to enable subsequent calculation (but not for display) by the following "worst case" approach:

- If the day of the end date is missing, the end date is set to last day of the month (or to the subject's trial completion date, if it is earlier than the last day of the month).
- If the day and month of the end date are missing, the end date is set to 31st of December of the year (or to the subject's trial completion date, if it is earlier than the 31st of December of the year).
- If the day of the start date is missing, the start date is set to first day of the month (except for investigator-prescribed SoC, where the first dosing day will be used if first dosing happened in the same month).
- If the day and month of the start date are missing, the start date is set to 1st January of the year (except for investigator-prescribed SoC, where the first dosing day/month will be used if first dosing happened in the same year).
- All other cases need to be assessed by the trial team on an individual basis, using the above points as guidance.

If a concomitant medication was ticked to be ongoing, it is expected that the end date is missing and will not be imputed for display purposes.

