SD	standard deviation
Min	minimum
Q1	lower quartile
Median	median
Q3	upper quartile
Max	maximum

Statistical parameters will be displayed to a defined number of decimal places as specified in the BI guideline "Standards for Reporting of Clinical Trials and Project Summaries " (*BI-KMED-BDS-HTG-0045*) ([10](#)).

Tabulations of frequencies for categorical data will include all possible categories and will display the number of observations in a category as well as the percentage (%) relative to the respective treatment. Percentages will be rounded to one decimal place. The category missing will be displayed if and only if missing values exist. Percentages will be displayed based on all subjects in the respective subject set regardless of the status of missingness.

Disposition of the patient population participating in the trial will be summarized by the frequency of subjects screened, randomized, screened but not randomized, randomized but not treated, randomized and treated, who completed randomized medication, who were prematurely discontinued from trial medication from randomized maintenance treatment, by reason, who received flare treatment at R1/D1 and at R3/D8 respectively, who completed flare treatment period, who were prematurely discontinued from flare treatment period, by reason, who received OL maintenance treatment, who completed the planned OL maintenance treatment and who were prematurely discontinued from OL maintenance treatment, by reason.

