For flare treatment period, if the selected treatment emergent adverse event did not occur, the time at risk will be censored at the end of the treatment period as defined in [Section 6.1](#).

For OL maintenance treatment period or overall period post any spesolimab use (i.e., i.v. or s.c.), if the selected treatment emergent adverse event did not occur, the time at risk will be censored at the end of the treatment period as defined in [Section 6.1](#) for OL maintenance phase.

For each selected treatment emergent AE, the exposure adjusted incidence rate will be calculated as:

Incidence rate [1/100 Subject years (pt-yrs)] =  $100 * \text{number of subjects with AE} / \text{Total AE-specific time at risk [subject years]}$ .

The analyses of AEs will be descriptive in nature. All analyses of AEs will be based on the exposure adjusted incidence rates (per 100 subject years), as well as the number of subjects with AEs and not on the number of AEs. System organ classes (if applicable) will be sorted according to the standard sort order specified by the EMA. Preferred terms (if applicable) will be sorted by total frequency (within system organ class) across all treatment columns.

For further details on summarization of AE data, please refer to "Handling and summarization of adverse event data for clinical trial reports and integrated summaries" (7) [001-MCG-156] and "Handling of missing and incomplete AE dates" (4) [BI-KMED-BDS-HTG-0035].

The analysis of AEs will be based on the concept of treatment emergent AEs. This means that all AEs will be assigned to the screening phase, applicable treatment phase or follow-up phase as defined in [Section 6.1](#).

An overall summary of AEs will be presented. This overall summary will also include summary for the class of investigator reported AESIs.

The following are considered as AESIs (see Sec 5.2.6.1 of CTP):

- Hepatic injury
- Systemic hypersensitivity reactions including infusion reactions and anaphylactic reaction
- Severe infections (according to RCTC grading in the ISF, selected laboratory parameters will be assessed by CTCAE in addition to RCTC grades, where possible)
- Opportunistic and mycobacterium tuberculosis infections

The investigator identified AESI will be captured from the eCRF and reported as “Investigator reported AESI” table.

In addition, user defined adverse event concepts (UDAEC) identified through specific search criteria will be reported separately ([Table 7.8.1:1](#)).

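### Laboratory abnormalities are compared between arms as crude percentages although laboratory data stop at open-label rescue, so the arms are not observed for comparable time

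*Protocol*

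**What the plan says.** Protocol Section 7.2.5 states, for patients who were rescued: "safety assessments including adverse events, laboratories, vital signs etc. which occurred subsequent to such intake will be excluded from presentations according to the planned treatments". Those data appear only in summaries of all data after any use of BI 655130. The same section compares treatment groups descriptively on laboratory distribution parameters and on the "frequency and percentage of patients with abnormal values or clinically relevant abnormal values".

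For adverse events the protocol goes further: "The exposure adjusted incidence rate (per 100 subject years) of a selected treatment emergent adverse event is defined as" patients with the event over total time at risk, and the date of rescue is one of the censoring dates. SAP Section 7.8.1 carries this over: "All analyses of AEs will be based on the exposure adjusted incidence rates (per 100 subject years), as well as the number of subjects with" at least one event. The protocol gives no such rule for laboratory abnormalities.

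The visible SAP text adds two general rules. Section 6.6.3 reads: "For safety data that is not collected by visit such as AE and possibly clinically significant laboratory abnormality, the original results (OR) to be used", in describing each treatment period. Section 7 reads: "Percentages will be displayed based on all subjects in the respective subject set regardless of the status of missingness". SAP Section 6.7 refers to a Section 7.8.2 for laboratory handling, which is not in the public text.

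**The concern.** A first flare calls for rescue, and rescue ends the period in which a laboratory value counts towards the randomised arm. A treatment that prevents flares therefore lengthens its own observation window. Protocol Table 7.5: 2 (Base) expects 2, 3, 6 and 16 first flares among 30 patients each on 300 mg q4w, 300 mg q12w, 150 mg q12w and placebo.

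The percentage of patients with at least one abnormal value rises with the number of draws. If placebo patients contribute far fewer draws, that percentage mixes laboratory risk with length of observation. The plan recognises unequal time at risk for adverse events, but the protocol's laboratory measure does not account for it. At stake is the reading of a descriptive safety table: with no test planned, readers will rely on the displayed percentages.

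**Working it through.** **Inputs.** From Protocol Section 7.5, Base scenario: placebo first-flare rate 17.1% per month for 3 months, then 3% per month; hazard ratios 0.1 (high), 0.15 (medium) and 0.3 (low); piecewise exponential; 30 patients per arm. Length: 48 weeks = 336/30.44 = 11.04 months. Flow Chart 1 schedules safety laboratory tests every 4 weeks, giving 12 post-baseline draws.

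**Assumptions not in the documents.** Rates are used as hazards, every flare is rescued at onset, and there is no dropout. The true risk of an abnormality is equal in all arms; 10% to 50% by week 48 was tried.

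**Step 1: reproduce the plan's event counts.** Cumulative placebo hazard is 3 × 0.171 + 8.04 × 0.030 = 0.513 + 0.241 = 0.754, so S(48 weeks) = exp(-0.754) = 0.470 and events = 30 × 0.530 = 15.9. The other arms give 6.1, 3.2 and 2.2. The total is 27.4, against the stated 16, 6, 3 and 2 and target of 27. About 12 of the 16 placebo events fall in the first 3 months: 30 × (1 - exp(-0.513)) = 12.0. The stated placebo median of 9.9 months is not matched exactly; the rounded rates give 3 + (0.693 - 0.513)/0.030 = 9.0.

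**Step 2: mean time observed before rescue**, the integral of S(t) from 0 to 48 weeks. For placebo: (1 - e^-0.513)/0.171 + e^-0.513 × (1 - e^-0.241)/0.030 = 2.35 + 4.28 = 6.62 months (rounded terms), which is 60.0% of 11.04.

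**Step 3: expected scheduled draws**, the sum of S(t) at weeks 4, 8, ..., 48.

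**Step 4: crude percentage at equal true risk of 20%.** Risk per draw p = 1 - 0.8^(1/12) = 1.84%. The chance of at least one abnormal value is averaged over the number of draws before rescue.

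| | Placebo | Low | Medium | High |
|---|---|---|---|---|
| Share of 48 weeks observed | 60% | 85% | 92% | 95% |
| Draws of 12 | 6.95 | 10.15 | 11.03 | 11.35 |
| Crude %, draws before rescue only | 11.7 | 17.0 | 18.4 | 18.9 |

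Counting the draw at R1 (the rescue visit, before infusion) at the same risk p gives 12.6% on placebo and 19.1% on high dose. A continuous-time version, λ∫S(t)e^(-λt)dt with λ = -ln(0.8)/11.04, gives 12.1% and 19.0%. High-to-placebo ratios are 18.9/11.7 = 1.62, 19.1/12.6 = 1.52 and 1.56. In continuous time the ratio is 1.57 at a true risk of 10% and 1.53 at 50%.

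**Step 5: range of the placebo window.** BasePlus 49%, BaseMinus 71%. Treating the Base rates as monthly probabilities gives 58%.

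**Step 6: effect of the time-at-risk rule.** At 20% true risk the rate is 0.0202 × 12 × 100 = 24.3 per 100 patient-years in every arm, so the artefact disappears.

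**Step 7: let the R1 draw carry a higher risk.** Flow Chart 2 schedules safety tests at R1, and Protocol Sections 5.2.3 and 6.2.2 place blood sampling before dosing. These values precede rescue intake, so Section 7.2.5 does not exclude them. Step 4 was repeated with only the risk at R1 changed:

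| Risk at R1 draw | Placebo | High |
|---|---|---|
| 1.84% (as other draws) | 12.6% | 19.1% |
| 10% | 16.8% | 19.6% |
| 16% | 19.8% | 20.0% |
| 30% | 26.9% | 21.0% |

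**The case against.** - **The direction is not fixed.** This stands. Protocol Section 1.1 links flares to neutrophilia, raised CRP and hypoalbuminaemia. Step 7 shows the gap closing at a 16% risk at the flare draw and reversing at 30%. A reader might infer that the laboratory tables are biased against spesolimab throughout, in dose order. The documents support that only for analytes the flare does not move.
- **The important signals already go through an adjusted route.** Largely true. Clinically relevant abnormal findings are reported as AEs (Protocol Sections 5.2.3 and 5.2.6.1.1), and hepatic injury defined by laboratory thresholds is an AESI (5.2.6.1.4). Both fall under the exposure-adjusted AE analysis. Values merely outside the reference range do not.
- **Other laboratory summaries are less affected.** True. Section 7.2.5 also compares distribution parameters, and SAP Section 6.6.3 plans by-visit summaries. Neither accumulates over unequal follow-up in this way.
- **The SAP may already deal with it.** This cannot be excluded. A reader might infer that the SAP has no adjustment, but Section 7.8.2 is not public and the visible rules do not settle it. Original results apply to AEs too, which are still exposure-adjusted, and the denominator rule is a general tabulation rule.
- **The numbers are small.** True. At 20% risk the gap is about 2 patients of 30, the spread across the active arms is about 0.6 of a patient (30 × (0.189 - 0.170)), and no hypothesis test is planned. The artefact is systematic, however, and without a test the displayed percentage is what gets read.

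**Conclusion.** The point holds against Protocol Section 7.2.5. Its crude percentage of patients with abnormal values compares arms expected to be observed for about 60% (placebo) and 95% (high dose) of 48 weeks, so it is not a like-for-like comparison. For analytes unrelated to flares, equal risk would appear as a ratio of about 1.5 to 1.6. For flare-driven analytes the distortion can cancel or run the other way.

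The 60% is a planning expectation, not a fact about the trial. It rests on the Base rates, rescue at the onset of every flare and no dropout. Flares treated with investigator-prescribed standard of care do not trigger the exclusion, so the real placebo share could be somewhat higher. The 20% risk is an assumption. The consequence is limited to a descriptive table, but the remedy is cheap enough that the change should be made.

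**What to change.** In Protocol Section 7.2.5, and in the SAP laboratory section if it does not already do so, compare patients with a first abnormal or clinically relevant value by the time-at-risk rule already defined for AEs. Use either the rate per 100 patient-years or a Kaplan-Meier cumulative incidence to week 48, censored at rescue. Keep the crude percentages as a supplement, footnoted with mean time at risk and number of draws per arm. Flag abnormalities found at the pre-infusion R1 draw so that flare-driven findings can be read separately.

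The cost is a sentence or two of text, reuse of the AE rate calculation on existing data, and one more column in the laboratory tables. The rate assumes a roughly constant risk over time; the Kaplan-Meier version does not need that assumption.

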7.2.7 Interim analyses

To support a potential BI655130 acute flare treatment submission, an interim analysis of the clinical efficacy and safety data collected during the BI 655130 OL i.v rescue treatment and s.c. maintenance treatment periods for GPP flare may be performed. The interim data snapshot will include the data from the i.v. rescue treatment period and OL maintenance treatment period. The initial randomized s.c. treatments will remain blinded and these data will not be analysed as part of this interim analysis. The timing of the interim analysis is driven by the timing of the submission of the acute flare treatment. Further details on the specifications for this interim analysis will be presented in the trial statistical analysis plan.

In order to ensure the patient's safety during the trial, a fully external DMC, independent of the trial and project teams, will review all available un-blinded safety data as well as selected efficacy data at regular intervals following first-patient-in. A DMC SAP which describes the analyses required for assessment by the DMC will be produced. Further details will be provided in a DMC charter.

7.3 HANDLING OF MISSING DATA

Every effort will be made to collect complete data at all visits. However, missing data will still occur and approaches to handle this are proposed below.

It is generally assumed that given the severity of a GPP flare, patients will always report to the investigator in a timely manner in order to ensure that proper treatment is received so that the developing flare can be rapidly treated. For the primary endpoint, only observed GPP flare events will be included in the primary analysis. No further imputation will be implemented on the missing values of GPPGA score and/or missing GPPGA pustule subscore. This will be the primary imputation method for the primary analysis. The same imputation strategy will be used for the two secondary endpoints, time to first worsening of PSS and time to first worsening of DLQI in the hierarchical testing procedure. The detailed censoring rules as outlined in [Table 7.3: 1](#) will be used.

Table 7.3: 1 Primary Method: Description of censoring rules for primary endpoint, and two secondary endpoints in hierarchical testing procedure

Situation	Outcome (event or censored)	Date of outcome
Without post randomization assessment		
No use of rescue medication or investigator-prescribed SoC	Censored	Date of randomization
The first use of rescue medication or investigator-prescribed SoC	Event	Date of the first use of rescue medication or investigator-prescribed SoC whichever comes earlier
With post randomization assessment		
No event, and, no use of rescue medication or investigator-prescribed SoC	Censored	Date of last assessment with no event confirmed
The first event, or the first use of rescue medication or investigator-prescribed SoC	Event	Date of first event, or the date of first use of rescue medication or investigator-prescribed SoC whichever comes earlier

The sensitivity analysis (Sensitivity Method) will utilize different rules to deal with missing values in the above-defined endpoints. The alternative censoring rules for sensitivity analysis are defined in [Table 7.3: 2](#).

For the primary analysis of the key secondary endpoint:

Missing GPPGA or GPPGA pustule subscores will not be imputed and only observed values will be utilized. If a patient is followed up to Week 48 and there is no flare, use of rescue medication or investigator-prescribed SoC reported, then this patient will be considered as a responder (i.e., no flare event) for the key secondary endpoint.

If for any reason, one or more patients are lost to follow-up or early discontinuation from the study before reaching the time-point of Week 48, then a sequential regression multiple imputation method will be implemented to impute the assessment of whether a flare event has

occurred by each visit at a binary level (Yes vs. No). This is a monotone increasing variable, so once a flare has occurred by a particular visit, all subsequent visits will also by definition have had a preceding flare. The imputation will include covariates, GPPGA subscore (pustules, scaling, erythema), as ordinal variables with values 0, 1, 2, 3 and 4. First, any non-monotone missing values will be imputed as the next observed value. Then the achieved monotone missing data will be imputed per the following steps:

1. Multiple Imputation of Missing data: A sequential logistic regression method is used to impute missing values of binary key secondary endpoint (Flare: Yes vs. No) at each visit.

For Visit 2, the GPPGA subscores (pustules, scaling, erythema) at Visit 2 as well as treatment, may be included as variables in the imputation model. If the assessment of a patient at Visit 2 is observed or imputed as a flare event, then the assessments of all subsequent visits of this patient will be imputed as flare events.

Visit 3 will be imputed in the same way but now including the GPPGA subscores (pustules, scaling, erythema) up to Visit 3, treatment and the response of patient at Visit 2 (Flare: Yes vs. No). All visits after an observed or imputed flare event with a flare event are again imputed as an event. Using the same approach, all visits will be imputed in order up to Visit 14 (Week 48).

2. Analysis of Completed Datasets: The imputed complete dataset will be used to perform the corresponding statistical analysis per permutation as specified in [Section 7.2.3](#).
3. Combine Results: PROC MIANALYZE combines the analysis results from step 2 and generates valid statistical inferences by accounting for the variability introduced by the MI process using Rubin's rules ([R12-2378](#)).

Further imputation rules for secondary endpoints and further endpoints will be described in TSAP if necessary. With respect to safety evaluations, it is not planned to impute missing values.

